6.0 Study Design and Procedures

Overview of Research Design. The proposed primary experiment (identical to K99MH109667) tests the hypothesis that perimenstrual E2+P4 withdrawal causes varying degrees of neuroactive steroid withdrawal, which produces co-occurring hopelessness and hyperarousal, which interact to cause proximal suicide risk. In a crossover placebo-controlled experiment, 90 completer female outpatients with recent SI (but acceptable suicide risk for outpatient treatment) will complete two counterbalanced perimenstrual conditions: (1) natural perimenstrual hormone withdrawal (placebo), and (2) prevention of perimenstrual hormone withdrawal (exogenous stabilization of E2+P4). Measures of neuroactive steroids, hopelessness, hyperarousal, and proximal suicide risk will be collected in the laboratory and via smartphone. The basic timeline for participation can be seen in Table 1a. We will utilize scientifically rigorous methods that promote transparency and reproducibility (NOT-OD-16-012): well-defined inclusion/exclusion criteria, validated measures, pre-registration of our protocol, and sharing of data.

Table 1a. Primary study activities and timeline.

STUDY TIMELINE	START	MONTH 1		MONTH 2				MONTH 3	MONTH 4				END	
	Enrollment Visit	Welcome Visit	Baseline Menstrual Cycle	STUDY PHASE 1 MENSTRUAL CYCLE				WASHOUT MENSTRUAL CYCLE	STUDY PHASE 2 MENSTRUAL CYCLE					
				Week 1	Week 2	Week 3	Week 4		Week 1	Week 2	Week 3	Week 4		
Order A (Half of study participants will be randomly selected to do the Active phase first and the Placebo phase second)				Ovulating Testing	ACTIVE E2 + P4				Ovulating Testing	PLACEBO patch and pills			1 Hour Debriefing Visit	
Order B (Half of study participants will be randomly selected to do the Placebo phase first and the Active phase second)				Ovulation Testing	PLACEBO patch and pills				Ovulating Testing	ACTIVE E2 + P4				
Laboratory Visits (90 minutes)					XXXXX					XXXXX				
Evening Surveys (3-5 minutes)		X	X	X	X		X	X	X	X		X		
Daily Phone Call (1 min per day)							X					X		
Using "BiAffect" App Keyboard		X	X	X	X		X	X	X	X		X		
Using Metricwire App		X	X	X	X		X	X	X	X		X		
Wearing Oura Ring		X	X	X	X		X	X	X	X		X		

SUB-STUDY TIMELINE	START	MONTH 1		MONTH 2				END	
	Enrollment Visit	Baseline Menstrual Cycle	OBSERVATIONAL MENSTRUAL CYCLE						
			Week 1	Week 2	Week 3	Week 4			
Ovulation Testing				X					
Laboratory Visits (60 mins)					XXXXXX				
Evening Surveys (3-5 mins)		X	X	X		X			
Using "BiAffect" App		X	X	X		X			

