Using Metricwire App		X	X	X		X			

Table 1b. substudy activities and timeline.

The proposed substudy characterizes 1) normative cycle-related variation in neuroactive steroids and mRNA expression, and 2) group-related differences (i.e., past-month SI vs HC) in trajectories of GABAAR subunit change across the cycle. 60 healthy controls (HC) with no SI will be recruited to gain a completer number of 40 for a two-month long observational substudy, in which five lab visits across one menstrual cycle (timed identically to mirror the observations across one medication phase of the experimental trial) will capture baseline molecular/genetic changes for between-group comparisons. The basic timeline for participation can be seen in table 1b.

The **double-blind crossover experimental design** is identical to that used during the PI's recently-completed trial (K99MH109667; Fig. 6). The TOP (red) panel shows natural perimenstrual hormone withdrawal in the placebo condition; the BOTTOM (black) panel shows prevention of hormone withdrawal in the active E2+P4 stabilization condition. THIS IS NOT A CLINICAL EFFICACY TRIAL, but a RCT design will probe the effect of hormone withdrawal (vs. stabilization) on proximal suicide risk and mediators. Participants will be randomized to condition order A (see Table 1 above; Active E2+P4, washout cycle, then Placebo) or condition order B (Placebo, washout cycle, then Active E2+P4). Investigational Drug Services will manage the double-blind. In each two-week condition, participants will wear a weekly patch (E2 or placebo) and take a daily pill (P4 or placebo). Because this manipulation simply delays natural E2+P4 changes⁹⁶, and given our previous finding of benefit¹², this manipulation is *not expected to pose greater risk than a normal menstrual cycle*.

Timing and Duration. Participants will receive the first seven-day transdermal E2 patch (or placebo patch) and begin daily oral P4 (or oral placebo) at a lab visit scheduled seven days after a positive urine ovulation test (+7 in Fig 6). This coincides with a time in the natural cycle when E2+P4 are already elevated. The weekly patch will be changed at the lab visit on day +14. The goal of this E2+P4 manipulation is to extend and maintain the mid-luteal phase hormone profile beyond the point in the cycle (i.e., around day +10) that would normally be associated with natural hormone withdrawal. Therefore, the active condition effectively prevents perimenstrual E2 and P4 withdrawal.

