10.0 Data Analysis and Statistical Considerations

ANALYTIC STEPS

For each outcome, we will use model fit indices to select the best-fitting hierarchical model before proceeding with analyses. Based on our prior study (K99MH109667) with a similar experimental design and similar data collection structure for daily surveys and lab visits, we expect that the data structure for primary analyses will be observations nested within participants (two-level regression model). In our prior models, inclusion of a third level of nesting (i.e., observations nested within condition nested within individuals) did not improve model fit and did not substantively alter hypothesis tests. Based on the prior study, we also expect that a combination of a random intercept for participant and an autoregressive (day-1) within-person error structure will be included based on model fit.

Testing Experimental Effects: Aim 1 and 2 require that we first evaluate the impact of the experiment on each of the 3 primary suicide outcomes and 9 (RDoC, neurosteroid) mediators described above. Therefore, we will first examine effects of the within-person hormone stabilization experiment on repeated measures outcomes across the menstrual cycle.

1. **For daily outcomes**, we will utilize multilevel models (with 52 days—26 per condition--nested within each individual; two-level models) to predict each repeated measures outcome from covariates (daily pain, illness, PRN medication use) and the interaction between (1) **experimental condition** (a dichotomous variable coded as 0 for natural hormone withdrawal condition and 1 for hormone stabilization condition) and (2) **condition phase**, a categorical (contrast) variable coded as follows: *midluteal baseline phase*, coded as days +1 to +7 after the positive ovulation test, *perimenstrual experimental phase*, coded as days +11 to +17 after the positive ovulation test, and the *medication withdrawal phase*, coded as days +22 to +26 after positive ovulation test (see Figure 6 in grant for study design and timeline). **Number of daily observations per person.** For the primary contrast between the midluteal and perimenstrual experimental phases, there are 28 observations per person—14 per condition (7 midluteal, 7 perimenstrual). Based on our preliminary data from the K99 trial (identical experimental manipulation), we anticipate receiving an average of 24 observations per participant.

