For each outcome, we will use model fit indices to select the best-fitting hierarchical model before proceeding with analyses. Based on our prior study (K99MH109667) with an similar experimental design and similar data collection structure for daily surveys and lab visits, we expect that the data structure for primary analyses will be observations nested within participants (two-level regression model). In our prior models, inclusion of a third level of nesting (i.e., observations nested within condition nested within individuals) did not improve model fit and did not substantively alter hypothesis tests. Based on the prior study, we also expect that a combination of a random intercept for participant and an autoregressive (day-1) within-person error structure will be included based on model fit.

Testing Experimental Effects: Both of our two aims require that we first evaluate the impact of the experiment on each of the 3 primary suicide outcomes and 9 (RDoC, neurosteroid) mediators described above. Therefore, we will first examine effects of the within-person hormone stabilization experiment on repeated measures outcomes across the menstrual cycle.

- a. For daily outcomes, we will utilize multilevel models (with 52 days—26 per condition-nested within each individual; two-level models) to predict each repeated measures outcome from covariates (daily pain, illness, PRN medication use) and the interaction between (1) experimental condition (a dichotomous variable coded as 0 for natural hormone withdrawal condition and 1 for hormone stabilization condition) and (2) condition phase, a categorical (contrast) variable coded as follows: *midluteal baseline phase*, coded as days +1 to +7 after the positive ovulation test, *perimenstrual experimental phase*, coded as days +11 to +17 after the positive ovulation test, and the *medication withdrawal phase*, coded as days +22 to +26 after positive ovulation test (see Figure 6 in grant for study design and timeline). Number of daily observations per person. For the primary contrast between the midluteal and perimenstrual experimental phases, there are 28 observations per person—14 per condition (7 midluteal, 7 perimenstrual). Based on our preliminary data from the K99 trial (identical experimental manipulation), we anticipate receiving an average of 24 observations per participant.

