- b. For laboratory visit outcomes, we will again utilize multilevel models (with 6 labs per person—3 per condition—nested within individuals; two-level models). A two-level model will predict each repeated measures lab outcome from covariates (daily pain, illness, PRN medication use) and the interaction between (1) experimental condition (a dichotomous variable coded as 0 for natural hormone withdrawal condition and 1 for hormone stabilization condition) and (2) condition phase, a categorical (contrast) variable coded as follows: *midluteal baseline visit, perimenstrual experimental visit*, and the *medication withdrawal visit*. Number of lab observations per person. For the primary contrast between the midluteal and perimenstrual experimental phases, there are 4 observations per person—2 per condition. Based on our preliminary data from the K99 trial (identical experimental manipulation), we anticipate very minimal missing laboratory data (see grant for details) but have estimated that on average each completer participant will miss .25 visits.
- c. **Hypothesized Pattern of Effects for Daily and Lab outcomes**: A significant interaction between experimental condition and condition phase is hypothesized for all twelve specified outcomes such that, in the natural withdrawal condition we expect deleterious changes from the midluteal phase to the premenstrual and menstrual phases (due to corresponding hormone withdrawal), but in the hormone stabilization condition we expect no deleterious

1 R01 MH120843-01 (PI: [name])

changes (or less severe changes) from the midluteal to the premenstrual and menstrual phases (since hormone withdrawal is prevented).

2. Testing Associations Between Mediators and Suicide Outcomes: Each aim next requires that we evaluate the day-to-day or week-to-week associations between single mediators (listed above) and suicide outcome variables on the same day or visit. This will be carried out in similar multilevel models as above, predicting each of the three primary suicide outcomes from person-centered values for each of the 9 mediators (listed above).

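### The daily and lab models omit period and period x phase although condition order is randomised; adding both closes a possible small bias at almost no cost

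*SAP*

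**What the plan says.** Protocol section 6.0 makes order the randomised factor: "Participants will be randomized to condition order A" (active, washout cycle, placebo) or order B (placebo, washout cycle, active). Table 1a states the ratio: "Half of study participants will be randomly selected to do the Active phase first and the Placebo phase second", and the other half the reverse. The same table puts the two study cycles in months 2 and 4.

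The SAP's Analytic Steps, part a, model daily outcomes "to predict each repeated measures outcome from covariates (daily pain, illness, PRN medication use) and the interaction between (1") condition and (2) phase, where phase has three levels (midluteal, perimenstrual, medication withdrawal). Part b does the same for visits: "A two-level model will predict each repeated measures lab outcome from covariates (daily pain, illness, PRN medication use") and the condition x phase interaction. Protocol section 10.0 repeats the list, again "to predict each repeated measures outcome from covariates (daily pain, illness, PRN medication use") plus that interaction.

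The hypothesis test is the interaction, read "For the primary contrast between the midluteal and perimenstrual experimental phases". On covariance, the SAP expects that "a combination of a random intercept for participant and an autoregressive (day-1) within-person error structure will be included based on model fit", and reports that in the prior trial "inclusion of a third level of nesting (i.e., observations nested within condition nested within individuals) did not improve model fit". Neither document names a period, order, sequence or carryover term. The model-fit step concerns nesting and error structure, so it would not bring one in.

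**The concern.** In a two-period crossover each participant contributes one cycle per condition, and randomised order is what separates condition from calendar position. Participants enter because of past-month ideation, under outpatient care, and the two study cycles are separated by a washout cycle. Ideation, or its perimenstrual rise, could well differ between the first and second study cycle through regression toward the mean, ongoing treatment or habituation to daily rating.

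If it does and the model has no term for it, two things can follow. The period effect stays in the residual and makes the test less sensitive. And if the orders are unequal among those analysed, part of a period effect may be read as a condition effect. The question is which kinds of period effect reach the contrast that is tested, and by how much.

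**Working it through.** **Inputs from the documents.** SAP power analysis: 85 completers, 24 daily observations each, ICC .64 for suicidal ideation, f² = .10, one-sided alpha .004, 3 predictors. SAP part a: 7 midluteal and 7 perimenstrual days per condition. Protocol sections 4.0 and 4.1: 170 recruited for 90 completers. The documents give no period-effect size and no completion by order. Values of d and delta below are assumptions, in within-person residual SD.

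**1. The SAP's own figure.** Effective N = 85 x 24 / (1 + 23 x .64) = 129.8 (SAP: 130). Power from the noncentral t with noncentrality sqrt(.10 x 129.8) is .816 (SAP: .81). The figure reproduces.

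**2. A period shift d that is constant across the cycle.** It adds d to both the midluteal and the perimenstrual days of the second cycle, so the within-cycle change is untouched. A noise-free random-intercept GLS fit (ICC .64, complete data, d = .5, split 50/35, no period term) gives a condition x phase bias of 0.000; only the condition main effect moves, by -.088. With about 14% of days missing at random the bias averages .001 or less in absolute value.

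The shift does stay in the residual. Half the days sit d/2 above and half d/2 below, so within-person variance is multiplied by 1 + d²/4. Dividing f² by that factor:

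| d | variance factor | power, suicidal ideation |
|---|---|---|
| 0 | 1.000 | .816 |
| .2 | 1.010 | .811 |
| .3 | 1.023 | .805 |
| .5 | 1.063 | .786 |
| 1.0 | 1.250 | .700 |

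**3. A period effect that differs by phase.** Let delta be the extra perimenstrual change in the second cycle. Without a period x phase term, the absolute bias in condition x phase is delta x |nA - nB|/n:

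| completers A/B | (nA - nB)/n | bias, delta = .3 | bias, delta = .5 |
|---|---|---|---|
| 43/42 | .012 | .004 | .006 |
| 50/40 | .111 | .033 | .056 |
| 50/35 | .176 | .053 | .088 |
| 60/30 | .333 | .100 | .167 |

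The GLS fits at delta = .3 agree for the three splits run (43/42, 50/35, 60/30). Adding only a period main effect leaves the bias as it was (.053 at 50/35). Adding period and period x phase brings it to 0.000.

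**4. Effect of the omitted period x phase term on the standard error.** In the planned random-intercept model, with equal orders and AR(1) ignored, the added daily variance is delta²/16 if the effect is centred over phases, or delta²/8 if it falls only on perimenstrual days. At delta = .25 the SE rises by sqrt(1 + .0039) to sqrt(1 + .0078), or 0.2 to 0.4%. At delta = .5 it rises by sqrt(1 + .0156) to sqrt(1 + .0313), or 0.8 to 1.6%.

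**5. How unequal could the orders be?** As an illustration, suppose 85 + 85 were randomised and each completed with probability 90/170. The imbalance |nA - nB|/n then has median .05 and 95th percentile .14, and is at least as large as 50/40 in about 13% of trials.

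**6. Cost of the terms.** Phase has three levels, so period takes 1 degree of freedom and period x phase takes 2. Going from 3 to 6 predictors in step 1 moves power from .8159 to .8156.

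**The case against.** The best defence is that the tested effect is already a within-cycle change, so ordinary drift between cycles drops out. That stands: a reader might infer that any drift, combined with unequal orders, biases the result, and step 2 shows that it does not.

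Second, in a two-period crossover the SAP's third level, condition within person, is also cycle within person. It did not improve fit in the prior trial, which speaks against large level shifts, and fit will be examined again for each outcome. This makes the lower rows of the step 2 table less likely. It says little about a period effect that differs by phase, which is the only kind that biases the contrast.

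Third, a reader might take 170 recruited for 90 completers as heavy loss after randomisation. The documents do not support that. Eligibility is assessed at the enrolment visit (protocol 6.0), people found ineligible there are still paid (Participant Compensation), one exclusion is confirmed from baseline ratings (4.1, criterion 14), and a baseline cycle precedes the first condition. The 170 therefore allows for people who never reach randomisation. Post-randomisation loss is not stated, so step 5 is an illustration and not a forecast. Protocol section 7.0 does discontinue participants for severe mood change or imminent suicide risk, so loss related to order is possible, but no figure is given.

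Fourth, the bias is small against the effect sought. At delta = .5 and a 50/40 split it is .056 SD, while protocol section 2.0 puts the prior trial's effect at roughly one person-standard-deviation. This also stands.

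**Conclusion.** The omission is real and runs through both documents, but its likely effect on the primary contrast is modest. A level shift between cycles costs some power and produces no bias; suicidal ideation has the least margin, and falls just under 80% at an assumed 0.5 SD shift. Bias arises only if the period effect differs by phase and completer orders are unequal, and is then delta x (nA - nB)/n. Both quantities are unknown from the documents.

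A reader might also infer that leaving out period x phase widens the standard error substantially. That would hold for an analysis of one contrast per person, not for the random-intercept model the SAP expects, where the increase is at most about 1.6% at delta = .5 (AR(1) ignored).

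The case for change rests on the balance of cost and protection: the terms use a factor the trial already randomises, they remove a possible bias, and they should be fixed before the data are seen.

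**What to change.** In SAP Analytic Steps parts a and b, and the matching paragraphs of protocol section 10.0, add fixed effects for period (first or second study cycle) and period x phase to every daily and lab model, and state that the condition x phase effect is reported adjusted for them. Both terms are needed. Report the number randomised and the number completing by order, so that the balance can be seen.

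The cost is a wording change and three degrees of freedom per model, with power for suicidal ideation unchanged at .816 to three decimals. No new data are required.

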Preliminary Data: Perimenstrual E2+P4 withdrawal (vs. stabilization) increases daily hopelessness. In our recent trial (K99MH109667), we found that ovarian steroid withdrawal (under placebo) was associated with *increased* daily reports of hopelessness in females with past-month SI, and that this was prevented by administering stabilizing doses of E2+P4 (Condition X Phase $\gamma = -.73$, $p = .023$). Further, controlling for daily within-person changes in hopelessness partially mediated the effect of E2+P4 stabilization on SI severity (95% CI for Indirect Effect: -.21 to -.53). *This preliminary work supports the premise that E2+P4 withdrawal causes perimenstrual hopelessness, effects which may explain proximal perimenstrual risk for suicide.*

Premise for Aim 1c

Hyperarousal as a Mediator of E2+P4 Withdrawal Effects on Suicide Risk

Hyperarousal, defined as physiological hyperarousal, psychomotor agitation, and agitation or overwhelm³², is an acute precipitant of suicidal behavior³²⁻³⁵. In a meta-analysis, disturbances in arousal were among the strongest predictors of suicidal behavior²⁵; however, this is an understudied area. In a meta-analysis focused specifically on *agitation*, agitation predicted suicide attempts³⁵. However, little within-person work has been done to understand the time course of risk. Similarly, altered cardiovascular reactivity is linked to SI and attempts³⁶⁻³⁸, but no work examines acute changes in physiological arousal and proximal suicide risk.

E2 and P4 withdrawal causes hyperarousal. In animals, E2+P4 withdrawal increases indices of hyperarousal, including autonomic function³⁹ and heightened behavioral reactivity to stimuli¹⁰. Withdrawal from neuroactive steroids, which occurs to varying degrees during E2+P4 withdrawal in the perimenstrual phase, causes reactivity-promoting alterations in associated brain circuitry, including the amygdala⁴⁰⁻⁴², the bed nucleus of the stria terminalis^{42,43}, and the periaqueductal grey^{44,45}. Further, variables linked to suicidal ideation and behavior, including social stress⁴⁶ and isolation⁴⁷, lifetime abuse⁴⁸, impulsivity⁴⁹, Borderline Personality Disorder^{50,51}, and PTSD^{52,53}, intensify effects of E2+P4 withdrawal on GABAergic neuroactive steroids or hyperarousal.

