Preliminary Data: Perimenstrual E2+P4 withdrawal (vs. stabilization) increases daily hyperarousal. In the previous hormone stabilization trial¹², we found increased daily agitation⁵⁴ and overwhelm⁵⁵ during perimenstrual E2+P4 withdrawal under placebo, which was prevented by administering stabilizing doses of E2+P4 (Cond \times Phase $\gamma = -.87$, $p < .0001$; Cond \times Phase $\gamma = -.92$, $p < .0001$). Controlling for within-person levels of self-reported agitation on the Brief Agitation Measure partially mediated the effect of E2+P4 stabilization on SI severity (95% CI for Indirect Effect: -.30 to -.55) and probability of endorsing suicide planning²⁰ (95% CI for Indirect Effect: -.18 to -.34). *This work supports the premise that E2+P4 withdrawal causes hyperarousal in the form of self-reported agitation, which may explain proximal perimenstrual risk for suicide.*

Preliminary Data: Our recent meta-analysis demonstrates that the perimenstrual phase is robustly associated with the lowest parasympathetic nervous system activity, consistent with physiological hyperarousal during perimenstrual E2+P4 withdrawal. Our meta-analysis (under review) aimed to quantify within-person variations in measures of cardiac vagal activity (indices such as heart rate variability, that capture parasympathetic innervation of the heart) across different cycle phases. A literature search following the PRISMA-Statement yielded 38 empirical studies (N=1,018) reporting repeated measures of cardiac vagal activity in at least two cycle phases. We found a significant decrease in parasympathetic activity from the late follicular (stable P4 and neuroactive steroids) to the premenstrual phase ($d = -1.32$, 95% CI [-2.35, -0.29]) during E2+P4 withdrawal. *This meta-analysis supports the premise that autonomic hyperarousal is heightened during perimenstrual E2+P4 withdrawal. The proposed trial would experimentally test if physiological hyperarousal is caused by E2+P4 withdrawal, and whether these changes mediate effects on suicide risk.*

[figure not shown]

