AIM 1: To evaluate hyperarousal and hopelessness as interacting mechanisms by which perimenstrual E2+P4 withdrawal (vs. experimental stabilization) increases proximal suicide risk. We predict that **(1a)** individuals will demonstrate greater proximal suicide risk during perimenstrual E2+P4 withdrawal (placebo) than during perimenstrual E2+P4 stabilization, an effect mediated by **(1b)** indices of hyperarousal, **(1c)** indices of hopelessness, and **(1d)** their interaction (i.e., with hopelessness predicting suicide risk only during hyperarousal).

AIM 2: To evaluate neuroactive steroid withdrawal as a mechanism by which perimenstrual E2+P4 withdrawal (vs. stabilization) increases proximal suicide risk. We expect that E2+P4 withdrawal (vs. stabilization) will induce neuroactive steroid withdrawal to some degree in all participants. However, we predict that the effect of hormone withdrawal (vs. stabilization) on proximal suicide risk at each lab will be mediated by **(2a)** degree of reduction in serum neuroactive steroid levels and **(2b)** degree of reduction in mRNA expression for neurosteroidogenic enzymes. We will also evaluate

within-person links between neuroactive steroids and all behavioral constructs; if appropriate, a multilevel mediation model will test the full model in Fig. 1.

AIM 3: To characterize GABA_{AR} gene expression plasticity across the cycle in individuals with and without perimenstrual changes in affective and suicide risk. In the HC group, we hypothesize that gene expression for $\alpha 4$ and δ subunits (GABRA4 and GABRD genes, respectively) are upregulated and $\gamma 2$ (GABRG gene) is downregulated in the midluteal (high ALLO) and perimenstrual (ALLO decline) phases compared to the midfollicular phase (low ALLO). We also hypothesize that clinical group moderates the effect of cycle phase on GABA_{AR} composition, such that the group with perimenstrual increases in affective symptoms and suicide risk shows higher slope of midluteal-to-perimenstrual change in $\alpha 4$ and δ subunits, and lower $\gamma 2$ subunit replacement of δ subunit expression than the HC group.

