3. Testing Interactive Effects of Hopelessness and Arousal on Suicide Outcomes: Interactions among hopelessness and arousal will be examined as predictors of suicide outcomes and as mediators of the experimental effect. In order to test this, we examine day-to-day interactive effects of daily person-centered hopelessness (noted above) and daily person-centered arousal indices (noted above) predicting same-daily suicide outcomes (noted above). We predict that higher-than-usual hopelessness on a given day will predict greater same-day risk on suicide outcomes, but only when arousal is *also* higher than usual for that individual.

4. Evaluating Mediation Where Appropriate. Finally, each aim indicates that **mediation** will be explored as appropriate. Only when analyses indicate significant effects of the experiment on both the suicide outcome and any mediator, as well as significant associations between the person-centered variable (or interaction variable) and the suicide outcome, we will utilize methods provided by **Bauer**, **Preacher**, **and Gil (2006)** to construct a confidence interval for the level 1 indirect effect of experimental condition (condition X phase) on the suicide outcome via the mediator.

1 R01 MH120843-01 (PI: [name]) POWER ANALYSIS.

With the funds allowed in this four-year grant, we are able to increase our proposed sample size slightly, from 80 to 85 completers, which would allow us to achieve 80% power to detect conventionally small-to-medium sized effects that, in our estimation, are clinically meaningful (i.e., $f^2 = .10$, which would mean that the interaction of condition and phase had uniquely accounted for 10% of the variance in the outcome in the perimenstrual window; Selya et al., 2012, "A Practical Guide to Calculating Cohen's f², a Measure of Local Effect Size"). We posit that if hormone withdrawal (vs. experimental stabilization) does not account for at least 10% of the variance in the outcome during this critical risky window of the menstrual cycle, then this line of research, which involves significant participant burden, is not worth pursuing further.

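### The plan specifies only one-mediator-at-a-time indirect effects for daily hopelessness and daily agitation, so the two estimates can overlap and cannot be read as two distinct mechanisms

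*SAP*

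**What the plan says.** Protocol section 3.0 states Aim 1 as "To evaluate hyperarousal and hopelessness as interacting mechanisms". It makes separate mediation claims for hyperarousal (1b), hopelessness (1c) and their interaction (1d). Section 2.0 attaches the letters b and c the other way round; the section 3.0 lettering is used here.

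The SAP (Analytic Steps, repeated in protocol section 10.0) proceeds as follows:

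- Step 2 will "evaluate the day-to-day or week-to-week associations between single mediators (listed above) and suicide outcome variables on the same day or visit", with each of the nine mediators person-centered.
- Step 3 brings hopelessness and arousal into one model: "Interactions among hopelessness and arousal will be examined as predictors of suicide outcomes and as mediators of the experimental effect".
- Step 4, if the earlier tests are significant, will "construct a confidence interval for the level 1 indirect effect of experimental condition (condition X phase) on the suicide outcome via the mediator".

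Protocol section 3.0 adds, under Aim 2, that "if appropriate, a multilevel mediation model will test the full model in Fig. 1". The Project Summary has a similar conditional sentence. Neither the SAP nor protocol section 10.0 specifies that model or says what would trigger it.

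Protocol section 6.0 (Daily Symptoms Survey) places the Brief Agitation Measure and the three Beck hopelessness items in the same evening questionnaire.

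**The concern.** Two self-reported distress scores, completed by the same person in the same sitting, can be expected to rise and fall together. When only one is in the outcome model, its coefficient picks up whatever part of the other's association with suicidal ideation it shares. The indirect effect built on that coefficient inherits the excess.

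The prior trial reports that both scores responded to the manipulation in the same direction, so both are likely to meet the treatment-to-mediator part of the step 4 condition. A score with no effect of its own could then also meet the mediator-to-outcome part through its correlation with the other, and be reported as a second mechanism. In a trial whose purpose is to identify mechanisms, that is an error of attribution. It also overstates how much of the hormone effect is explained if the two figures are added. The tests of the experimental effect on each outcome are not touched.

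**Working it through.** **Inputs** (protocol section 2.0, prior trial, absolute values)

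- Total condition x phase effect on ideation severity: T = .75, p < .0001, no interval given.
- Condition x phase effect on hopelessness: a_H = .73 (p = .023). On agitation: a_A = .87 (p < .0001).
- Indirect effect through hopelessness: "95% CI for Indirect Effect: -.21 to -.53". Through agitation: "95% CI for Indirect Effect: -.30 to -.55".
- Within-person same-day correlation r of the two scores: not given. Assumed range 0 to .7.

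The documents state no point estimate for either indirect effect, no sum and no proportion mediated, so there is no stated figure to reproduce. What follows is derived.

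**1. Do the prior-trial figures fit overlap?**

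Midpoints: (.21 + .53)/2 = .370, or .370/.75 = 49% of T; (.30 + .55)/2 = .425, or 57% of T.

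Sum: .370 + .425 = .795, and .795/.75 = 106%.

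Lower limits added: .21 + .30 = .51 (68%). Upper limits added: .53 + .55 = 1.08 (144%).

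Standard errors from interval widths: .32/3.92 = .082 and .25/3.92 = .064. The sum has an approximate 95% interval of .59 to 1.00 if the two estimates are independent, and .52 to 1.07 if they correlate .8. With T held at .75, the chance that the sum exceeds it is about 63% to 67%. T is itself uncertain: p < .0001 only bounds its standard error at .75/3.89 = .19.

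**2. How much could an inert mediator be credited?**

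Implied mediator-to-outcome slopes: b_H = .370/.73 = .507; b_A = .425/.87 = .489. This assumes one scale for all the coefficients and similar within-person variances of the two scores.

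Suppose only agitation acts. The lone hopelessness slope is then r x b_A, and its apparent indirect effect is a_H x r x b_A:

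- r = .3: .73 x .3 x .489 = .11 (14% of T)
- r = .5: .73 x .5 x .489 = .18 (24% of T)
- r = .7: .73 x .7 x .489 = .25 (33% of T)

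At r = .5 this is .18/.425 = 42% of the agitation effect. In the reverse case, an inert agitation score would show .87 x .5 x .507 = .22, or 60% of the hopelessness effect of .370.

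**3. What would joint entry do to the prior-trial midpoints?**

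b_H,joint = (b_H - r b_A)/(1 - r²), likewise for agitation, each multiplied by its a-path:

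| assumed r | hopelessness | agitation | sum | share of .75 |
|---|---|---|---|---|
| 0 | .370 | .425 | .795 | 106% |
| .3 | .289 | .322 | .611 | 81% |
| .5 | .256 | .273 | .528 | 70% |
| .7 | .236 | .228 | .464 | 62% |

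(Sums are from unrounded values. This calculation has no product term.) At r = .5 the lone estimates are about 1.45 times (hopelessness) and 1.56 times (agitation) the joint ones.

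**4. Is the common scale safe?** Not clearly. The hopelessness a-path at p = .023 has z of about 2.27, while its indirect-effect interval implies z = .370/.082, about 4.5. A simple product of coefficients cannot have a larger z than its a-path. A different scale or model, or a random-effect covariance term, may explain this. The percentages in parts 1 to 3 are therefore illustrations.

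**The case against.** The plan does not ignore joint modeling. Step 3 puts hopelessness and arousal in one model, and steps 3 and 4 allow the interaction itself to be tested as a mediator, so it would be wrong to call step 3 merely an association test. The full path model is also foreseen. This stands, and it narrows the gap. But step 3 serves claim 1d, does not say that both main effects enter, and is not named as the source of the 1b or 1c indirect effects. The path model is conditional and unspecified.

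A reader might infer that the prior trial already shows the two mediators explaining more than the whole treatment effect. The documents do not support that. The 106% rests on derived midpoints, the limits run from 68% to 144%, and a shared scale is not stated and is in some doubt. Even a true sum above 100% would not prove overlap, since an opposite-signed direct path could also produce it. Nor do the documents expressly say that each prior-trial mediator was modeled alone.

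A reader might also extend the point to all hyperarousal measures. Of the SAP's five arousal outcomes, only the Brief Agitation Measure shares the evening survey with hopelessness. The accelerometer, typing, RSA and PEP measures do not.

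Finally, mutual adjustment is not neutral. If one symptom drives the other, adjustment removes a real part of its effect, and same-day data cannot settle the order. Section 2.0 also hypothesizes that hopelessness acts only in hyperaroused states, so a joint model without the product term would contradict the study's own theory. Both points stand and shape the fix.

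**Conclusion.** The concern holds for daily hopelessness and the daily Brief Agitation Measure. As written, the plan yields separate single-mediator indirect effects that can overlap, and it has no specified step to tell two mechanisms from one. This follows from the wording of steps 2 and 4 and does not depend on the prior-trial sum.

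The size is conditional. With the prior-trial a-paths, one scale, similar within-person variances and an assumed r of .5, an inert hopelessness path would show about .18, or 24% of .75 (14% at r = .3, 33% at r = .7). The prior-trial midpoint sum of about 106% is compatible with overlap and proves nothing more. If the true within-person correlation is near zero, the problem is small. The documents give no figure either way.

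**What to change.** In step 4 of the SAP, and the matching paragraph of protocol section 10.0:

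- Add one outcome model containing person-centered daily hopelessness, person-centered daily Brief Agitation Measure, their product, condition, phase and condition x phase.
- Report each adjusted indirect effect, their contrast and the total indirect effect beside the lone-mediator results. With the product in the model, each adjusted effect depends on the level of the other score, so state the levels used (for instance, the person's own mean).
- Describe hopelessness and agitation as separate mechanisms only where the adjusted effects support it.
- Report the within-person correlation of the two scores.
- Either specify the full path model and its trigger in the SAP or label it exploratory.

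The interval method, bootstrap or the one already named, can stay with the sponsor.

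No new data, visits or participants are needed. There are two statistical costs: wider intervals when the scores are highly correlated, and adjusted effects that understate a mediator acting through the other. The second is the reason to keep both sets of results.
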